2.10 PD and PK/PD analyses

Not applicable.

2.11 Subject-reported outcomes

Not applicable.

2.13 Interim analysis

In the third interim analysis, no DLT's in Part 1 were identified; this analysis will not be repeated in the upcoming fourth interim analysis of Parts 1 and 2 – details can be found in [Appendix 5.4.3](#).

3 Sample size calculation

Part 1

The sample size for Part 1 is driven by feasibility. In Part 1, cohorts of at least 2 subjects are planned to be dosed until a decision is made for MTD, however adjustment of cohort size might be considered due to enrollment and safety consideration. 13 subjects were enrolled to test 5 dose levels. At least 2 subjects are required for cohort 1 at the starting dose. Size of later cohorts may be adjusted based on feasibility. As noted earlier, if more than two subjects present simultaneously for the study, additional subject(s) may be dosed in a cohort to avoid unnecessary delays in treatment of this life-threatening disease.

Part 2

In Part 2, 25 subjects were enrolled to evaluate up to 2 different dose cohorts with at least 6 subjects and up to approximately 10 subjects per cohort.

The driver of the sample size in Part 2 is the primary objective, safety. We are able with 95% confidence to rule out that the true incidence rate exceeds 50% of any class of adverse events if none in that class are observed in 6 subjects.

Furthermore, in an interim analysis of CHOP INTEND data from Part 1, CHOP INTEND scores were analyzed by a mixed linear model with covariates for dose, baseline CHOP INTEND, and calendar age. A compound symmetric covariance structure was assumed for observations within the same individual. This analysis pointed to a total estimated variability of 7 on a CHOP INTEND scale (sum of between and within subjects' variance components). The table below ([Table 3-1](#)) shows the power to detect a difference in CHOP INTEND score between two adjacent dose groups (by one-sided t test at nominal significance level 5%). It seems likely that differences exceeding 10 points on a CHOP INTEND scale will be identifiable with the planned sample size.

Table 3-1 Power to detect a difference in CHOP INTEND score between two adjacent dose groups (by one-sided t-test at nominal significance level of 5 percent)

	N=6	N=7	N=8	N=9	N=10
Effect size 8 points	56%	64%	70%	74%	78%

Effect size 10 points	74%	80%	85%	89%	92%
12 points	86%	91%	94%	96%	98%

4 Change to protocol specified analyses

The following analyses were specified in the protocol but will not be performed or will be analysed differently:

- [REDACTED]

- The repeated measures analysis specified in section 11.5.1 (for part 1 and part 2 together, for continuous endpoint) was not performed. No repeated measures model was estimated.
- Listings for relevant medical history and current medical condition, concomitant therapies, [REDACTED] from the protocol will not be produced. Team assessed that tables with summary statistics are sufficient for the purpose of the CSR.
- The listing for laboratory will not display all data. Instead, if there is any value outside normal range of a parameter for a subject then all records for that parameter and this subject are listed.

[REDACTED]

[REDACTED]

- As time to death, permanent ventilation or tracheostomy is specified as efficacy assessment in the protocol summary, Kaplan Meier tables and plots for that endpoint will be provided, and not for time to death or permanent ventilation as specified in section 11.5.1 from protocol.

5 Appendix

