The diagnosis of SMA is usually prompted by referral for evaluation between 1 and 4 months of age (range: birth to 8 months). The diagnosis of Type 1 SMA is traditionally made on clinical grounds, ultimately dependent upon the demonstration that independent sitting is not achieved after a period of observation (EMA 2016). The patients in Part 1 of the study were aged between 1-7 months. Since newborn pre-screening is already in place in some countries, the age of the study patients in Part 2 will be defined as up to 180 days of age at screening.

Branaplam distributes to the brain in both rat and dog, both juvenile and adult animals, so significant brain penetration in infants is anticipated. If branaplam is to offer benefit, it is most likely to be in preserving motor neurons before they die off and thus age of patient at entry into study is crucial. The mechanism of action of branaplam is via increasing SMN protein in key cell types such as the alpha-motor neurons. Therefore, it is likely that branaplam will offer the maximal benefit if the target population of motor neurons are not irreversibly diminished, so recruitment for this study must be built around enrolling infants with SMA at the earliest stages of the disease process as possible.

Studies should be conducted in the patient population where there is the potential for benefit of the treatment. Novartis proposes that branaplam be tested in SMA patients with SMA Type I, because they suffer the most life-threatening form of SMA and have the greatest medical need for effective therapies and the highest prospect for direct benefit from participating in the planned study. By selection of 2 copy SMN2 SMA Type I patients, the study population is generally more homogeneous than other SMA types, which is anticipated to increase the probability to see treatment benefit in an open label study.

Patients with milder SMA Type II, III or IV have more slowly progressive disease, often characterized as a stable disease course. They typically survive to adulthood.

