11.5 Analysis supporting secondary objectives

11.5.1 Efficacy and/or Pharmacodynamics endpoint(s)

Secondary endpoints including growth measurements, respiratory function assessments, and CHOP INTEND infant motor scale, as well as their difference from baseline where a baseline is present, will be summarized at different time points for Parts 1&3 and Parts 2&3 separately.

Measurements which fall on a close to continuous scale (such as CHOP-INTEND and), the change from baseline will be analyzed by a mixed model for repeated measurements (MMRM) for study parts 2 and 3, with terms for treatment group, baseline value, baseline age category (<= 4 months/> 4 months), visit, treatment group*visit interaction, and baseline value*visit interaction.

Kaplan Meier plots for time to death or permanent ventilation will be provided with 95% confidence intervals.

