** Patients completing a total of 13 weeks of treatment will be considered to have completed the study and may continue treatment at the discretion of Novartis, the investigator and the independent DMC. Patients may be escalated to a higher dose cohort once that dose is deemed safe.

Table 1-1 Provisional dose levels for Part 1 dose escalation

Dose level	Provisional weekly dose	Increment from previous dose ^b
-2 ^a	1 mg/m ²	67% reduction
-1 ^a	3 mg/m ²	50% reduction
1	6 mg/m²	Starting dose
2	12 mg/m ²	100% increase
3	24 mg/m ²	100% increase
4	48 mg/m ²	100% increase
5*	60 mg/m ²	25% increase

^a Dose level -1 and -2 may be used if appropriate (e.g. if the **starting dose** level is not well tolerated)

^b The dose increase will be guided by BLRM. Up to 100% dose increase is permitted per dose level if the recommended dose increment is higher than 100%

* This weekly dose level 5 would convert into a 2.95 mg/kg dose of branaplam for a 6.5 kg, 62 cm subject with BSA of approximately 0.32m²

Table 1-1 is intended as an example for guidance for the dose escalation part only. Intermediate dose levels may be used, and some dose levels may be skipped if the dose-escalation rules presented in this protocol are followed. Actual dose levels will be confirmed in writing by Novartis and provided to all participating study sites before treatment of subjects in a new cohort.

In Part 1, the dose unit changed from a body surface-normalized unit (mg/m^2) to a body weight-normalized unit (mg/kg). The body weight-normalized doses will be used in all study reports. These will be labelled “nominal dose”.

Part 2

Part 2 of the study enrolled new subjects into one of 2 different dose cohorts; cohort 1 at 0.625 mg/kg and cohort 2 at 2.5 mg/kg with once weekly dosing for 52 weeks, as shown in **Figure 1-2** below. The branaplam dose was escalated in subsequent cohorts after 6 subjects have been enrolled or at least 3 subjects from the initial cohort have completed 13 weeks of treatment.

A total of 25 subjects have been enrolled into Part 2 and assigned to either of the two doses, previously tested in Part 1. It is designed to evaluate whether a change over time in infant and growth parameters can be detected and interpreted as an effect in branaplam treatment.

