1.1 Study objectives and endpoints

The purpose of Part 1 of the study was to evaluate the safety, tolerability, pharmacokinetics (PK), pharmacodynamics (PD) and efficacy; and to estimate the Maximum Tolerated Dose (MTD) of branaplam.

The purpose of Part 2 of the study is to characterize dose-exposure-response to inform dose selection of orally administered branaplam in subjects with Type 1 SMA.

The purpose of Part 3 of the study is to provide continuous treatment with branaplam to patients who have participated in Part 1 or 2 of the study and have completed at least 52 weeks of treatment. In addition, Part 3 provides long-term safety and efficacy follow-up for patients treated with branaplam for more than 52 weeks.

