2.1 Data analysis general information

A statistical vendor (CRO), [REDACTED] to which the statistical analysis is outsourced, will perform all planned analyses, i.e. IAs (Section 2.13) as well as the final analysis after the final database lock. Details of the analyses for Parts 1, 2, and 3 at the upcoming final database lock are outlined in this document.

Data will be analyzed using SAS® version 9.4 (or higher).

Descriptive summary statistics, unless otherwise specified, for continuous variables include number of non-missing observations (n), mean, median, standard deviation (SD), Q1 (25th percentile), Q3 (75th percentile), minimum and maximum, while for categorical variables frequencies and relative percentages will be reported.

Descriptive analyses will be stratified by part as follows:

- For disposition, demographics, baseline characteristics, and medical history, and protocol deviations, by parts (Part 1, Part 2, Part 1 & 2, Part 3)
- For all other summaries and figures: Part 1 & 3, Part 2 & 3, and Total (where applicable)

For analysis summaries, Part 1 will not be stratified by titration dose, while Part 2 will be stratified by the two treatment doses. For patients in Part 3 from Part 2, the fixed dose in Part 2 will be used as a strata; thus transitions from a low dose to a higher dose in Part 3 will not be analysed separately.

Individual graphs, such as spaghetti plots by study part and treatment and panel plots by study part and subject (with actual dose displayed as background shading) relative to time from first dose (in months) will be provided for selected endpoints, as applicable. Individual graphs relative to calendar age (in months) such as growth curve plots of vital signs, etc. will also be presented.

Listings will be provided by study part, cohort and subject.

The following treatment labels will be used for all tables, listings and figures in the order provided here:

- **Part 1:**
LMI070 0.3125 mg/kg, LMI070 0.625 mg/kg, LMI070 1.25 mg/kg, LMI070 2.5 mg/kg,
LMI070 3.125 mg/kg
- **Part 2:**
LMI070 0.625 mg/kg, LMI070 2.5 mg/kg
- **Part 3 (from Part 1):**
LMI070 0.625 mg/kg, LMI070 2.5 mg/kg, LMI070 3.125 mg/kg
- **Part 3 (from Part 2):**
LMI070 0.625 mg/kg, LMI070 2.5 mg/kg

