2.7.1 Secondary endpoint

The following efficacy endpoints will be summarized with appropriate descriptive tables over time by study part and in Parts 2 & 3, additionally by treatment group:

- CHOP INTEND infant motor total score
- Respiratory function assessments (respiratory rate, pulse oximetry, paradoxical breathing, breathing pattern [chest circumference measured during quiet breathing (sleep)])
- Growth measurements (body weight, head circumference, length and chest circumference)
- Ventilation status
- Preservation of oral feeding
- HINE motor total score

- Ability to sit without support at 12-months of treatment: This is part of the HINE, if a subject has the ITEM="Sitting" with Score 3 or 4 then they are considered as able to sit without support. See [Table 2-14](#) below.

For all continuous secondary endpoints, summary statistics for raw and change from baseline (when baseline is available), will be provided.

For the categorical secondary endpoints, frequencies and relative percentages will be reported.

Other secondary endpoints

- AUC and Cmax of branaplam

For PK analysis please refer to section 2.9.

A summary of the number of patients and relative frequencies of patients with and without tracheostomy at baseline, installed or removed during the study will be provided by part and cohort (for parts 2 & 3).

The number of patients who had a tracheostomy or permanent ventilation during the study and discontinued the study drug on/after the start of the event will be provided by part and cohort (for parts 2 & 3).

HINE-2 and the Motor and Speech Domains

The domains for the HINE-2 motor score are provided in [Table 2-14](#) below. If all subscores are "Did Not Test" (DNT) then the HINE Motor Total Score is missing. If at least one subscore is available, then any other DNT will be imputed as 0 in the sum for the HINE Motor Total Score derivation.

Note: HINE motor score information is available in two source datasets, MOT and QUE. Data from both datasets will be combined and used in the HINE data analysis.

Table 2-14 HINE-2 and the Motor and Speech Domains

Item	Score	Functional definitions and score						
		0	1	2	3	4	5	6
Head Control	Did Not Test	Unable to maintain upright	Wobbles	All the time upright				
Sitting	DNT	Cannot sit	Sits with support at hips	Sits with support (props)	Stable independent sit	Pivots (rotates)		

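### SAP section 4 drops the protocol's MMRM for Parts 2 and 3 with no visible reason and the wrong scope, leaving no visible Part 2 dose difference in CHOP INTEND adjusted for baseline score and age

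*SAP*

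**What the plan says.** Protocol 11.5.1 covers measures on a near-continuous scale, and CHOP INTEND is the only one legibly named. For these it says "the change from baseline will be analyzed by a mixed model for repeated measurements (MMRM) for study parts 2 and 3". The terms are treatment group, baseline value, baseline age category (cut at 4 months), visit, and the interactions of treatment group and baseline value with visit.

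SAP section 4, which lists departures from the protocol, says: "The repeated measures analysis specified in section 11.5.1 (for part 1 and part 2 together, for continuous endpoint) was not performed". It adds: "No repeated measures model was estimated". No reason is visible in that entry, although the entries on listings and on the Kaplan-Meier endpoint each give one.

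What remains for CHOP INTEND is descriptive. SAP 2.7.1 states: "For all continuous secondary endpoints, summary statistics for raw and change from baseline (when baseline is available), will be provided". SAP 2.1 adds that "Part 2 will be stratified by the two treatment doses". SAP 2.7.1 also plans median change by visit and baseline age group, bar charts of improvement by age group, responder tables and plots. The visible model section, 2.7.2, contains only the Kaplan-Meier analysis.

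**The concern.** SAP 1.1 states the aim: "The purpose of Part 2 of the study is to characterize dose-exposure-response to inform dose selection". The comparison that serves this aim is between two cohorts that were not formed by a described randomisation. On Part 2 the SAP says "The branaplam dose was escalated in subsequent cohorts after 6 subjects have been enrolled", or once at least three infants in the first cohort had completed 13 weeks. Protocol 5.5 assigns treatment numbers in ascending order. A visit heading in Protocol 3.2 contains the word randomisation, but no procedure follows it.

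Infants who entered at different calendar times may differ in age and baseline function. Protocol 3.4 regards age as prognostic: "thus age of patient at entry into study is crucial". The sponsor's own Part 1 interim model for CHOP INTEND adjusted for baseline score and calendar age (SAP section 3). If the cohorts differ on these variables, the unadjusted dose difference mixes that imbalance with dose. A reader would see the imbalance in the baseline tables. No visible output would show how far the dose difference moves once both variables are allowed for, or how precisely it is then estimated.

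The change record is also wrong. The SAP says it is consistent with protocol amendment 11, yet the scope it gives for the dropped analysis is not the amendment 11 scope.

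**Working it through.** **1. Scope, side by side.** Protocol 11.5.1: Parts 2 and 3. SAP section 4: Parts 1 and 2 together. The two do not agree. The amendment 11 log says the repeated-measures specification was updated, so the SAP wording may be a carry-over; that is inference.

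**2. The plan's own power figure.** SAP Table 3-1 (protocol Table 11-1) reproduces with a two-sample t test, one-sided 5%, SD 7 and equal groups. For 10 points at N = 6 to 10 per group I get 74.4, 80.9, 85.8, 89.5 and 92.3%, against 74, 80, 85, 89 and 92% stated. All 15 cells agree within 2 points. The SD of 7 comes from the Part 1 model with dose, baseline score and age as covariates. The table thus assumes a covariate-adjusted SD and a between-dose test, and the visible SAP plans neither an adjusted model nor that test.

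**3. What can still be derived.** The default statistics in SAP 2.1 (n, mean, SD) by dose allow an unadjusted difference and interval. Summaries by age group, read with the stratification by dose, can show part of any age confounding. Joint adjustment with baseline score and a model-based interval are not available.

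**4. Precision of an adjusted Week 52 difference.** Half-width = t(0.975, n1+n2−4) × SD × √[(1/n1 + 1/n2)/(1 − R²)], where R² is the share of dose assignment explained by baseline score and age, and the model has four mean parameters. The documents give 25 infants but not the split by dose, so the splits, R² and the SD of 10 are assumptions. SD 7 is the planning value.

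For 12/13 and SD 7: t = 2.080 on 21 df and √(1/12 + 1/13) = 0.4003, so 2.080 × 7 × 0.4003 = 5.83. Dividing by √0.8 gives 6.52; dividing by √0.6 gives 7.52.

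| Split, SD | R² = 0 | R² = 0.2 | R² = 0.4 |
|---|---|---|---|
| 12/13, SD 7 | 5.83 | 6.52 | 7.52 |
| 10/15, SD 7 | 5.94 | 6.64 | 7.67 |
| 10/10, SD 7 | 6.64 | 7.42 | 8.57 |
| 12/13, SD 10 | 8.33 | 9.31 | 10.75 |

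**5. What age imbalance could do to the unadjusted difference.** Shift = difference in the share aged ≤ 4 months × age effect. Age effects of 5 and 10 points are assumed.

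- 9/12 v 4/13: 0.750 − 0.308 = 0.442, so 2.2 and 4.4 points.
- 8/12 v 5/13: 0.667 − 0.385 = 0.282, so 1.4 and 2.8 points.
- 6/12 v 6/13: 0.500 − 0.462 = 0.038, so 0.2 and 0.4 points.

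**6. Coverage.** In 20,000 simulated trials per case (residual SD 7, no true dose effect), the unadjusted nominal 95% interval covers about 90% and 80% at 9/12 v 4/13, and about 94% and 92% at 8/12 v 5/13. ANCOVA covers about 95%, but that follows from the set-up: age is the only confounder simulated, it is in the model, and baseline score is unrelated to outcome. Adding an assumed unmeasured cohort effect of 3 points brings ANCOVA coverage down to the low-to-mid 80s per cent. The simulation says nothing about the value of adjusting for baseline score.

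**The case against.** The case against has weight. Both documents call all parts non-confirmatory. The omission is disclosed in the section meant for such changes, and its second sentence leaves no doubt that no repeated measures model exists. Age is partly handled by the descriptive age-group summaries, although the named table gives medians and SAP 2.2.1 limits subgroups to selected analyses. Part 2 entry was capped at 180 days of age with a minimum CHOP INTEND score of 15, which limits the imbalance possible. Even the largest shift shown, 4.4 points, is smaller than every half-width in the table. The 52-week comparison has already been made in open-label data, so any model added now is post hoc. An ANCOVA would not be the protocol's MMRM.

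Most of this stands and limits the point to interpretability; type I error is not at issue. It does not explain the missing reason or the wrong scope. It also does not supply a dose difference that allows for both covariates. Small numbers are an argument for a simple model and an honest interval, and could have been given as the reason for the omission.

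Three stronger readings are tempting. A reader might infer that the choice of dose for Part 3 rested on unadjusted CHOP INTEND data; Protocol 3.5.3 instead cites HINE-2 changes, comparable safety and target engagement. A reader might infer that the SAP contains no adjusted analysis at all; section 4 has redacted items and section 2.12 is redacted, so only the visible text can be judged. A reader might infer that the MMRM was promised for all motor scores; the legible protocol text names CHOP INTEND and then breaks off.

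**Conclusion.** The concern holds in limited form. The protocol's adjusted model for Parts 2 and 3 is dropped, the visible entry gives no reason, and its scope is misdescribed. For CHOP INTEND in Part 2, the clear loss is joint adjustment for baseline score and age with a model-based interval. Confounding by age alone can be partly seen in the planned descriptive tables.

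The size is uncertain. The shifts in step 5, from 0.2 to 4.4 points, illustrate assumed age shares and effects; they are not estimates for this trial. The precision figures depend on an assumed split and on an SD taken from Part 1 scores, not from Part 2 Week 52 change. Adjustment would bring the estimate closer to the dose effect only as far as age and baseline score account for the difference between cohorts. This should be corrected, but it does not invalidate the plan.

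**What to change.** 1. In SAP section 4, correct the scope to Parts 2 and 3 and state why the MMRM is omitted.
2. In SAP 2.7.2, add one exploratory estimate of the 2.5 minus 0.625 mg/kg difference in CHOP INTEND change from baseline at Week 52, with a 95% CI. Analyse by initial Part 2 dose, adjusted for baseline score and age category (≤ 4 / > 4 months). Name one model before it is run: ANCOVA, or a compound-symmetry repeated measures model through Week 52. Label the estimate non-randomised and applying to infants alive and assessed.
3. Beside it, show by dose the number lost before Week 52 and the number whose dose changed within Part 2. SAP 2.8.3 plans deaths by study part only.
4. Do not use exclusion of data after a dose change as a check on bias. Under Protocol 5.4.3 that change is triggered by loss of motor score, so exclusion selects on the outcome. If it is shown, say so.
5. HINE-2 is optional and should be labelled a new analysis.

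The cost is a few tables and two sentences. The age group, the Week 52 window and the dose strata are already defined in the SAP. The downsides are a wide interval and residual confounding by cohort and calendar time that two covariates cannot remove.

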5.1 Imputation rules

In any analysis or evaluation, if the visit date(s) is missing, no imputation will be implemented.

5.1.1 Study drug

Start date and end date of study drug on the respective CRF panel are mandatory; thus, no date imputation will be applied.

5.1.2 AE and concomitant medication date imputation

Incomplete start date or end date of an adverse event or concomitant medication taken will be handled by following rules:

Table 5-1 Imputation of start dates (AE, CM)

Missing Element	Rule
day, month, and year	
• No imputation will be done for completely missing dates
day, month	
• If available year = year of study treatment start date then
◦ If end date contains a full date and end date is earlier than study treatment start date then set start date = 01JanYYYY◦ Else set start date = study treatment start date.• If available year > year of study treatment start date then 01JanYYYY• If available year < year of study treatment start date then 01JulYYYY
day	
• If available month and year = month and year of study treatment start date then
◦ If end date contains a full date and end date is earlier than study treatment start date then set start date= 01MONYYYY.◦ Else set start date = study treatment start date.• If available month and year > month and year of study treatment start date then 01MONYYYY• If available month and year < month year of study treatment start date then 15MONYYYY

Table 5-2 Imputation of end dates (AE, CM)

Missing Element	Rule (* = min(death date, safety cutoff date, withdrawal of consent date))
day, month, and year	
• Completely missing end dates (incl. ongoing events) will be imputed by the end date of the on-treatment period*

Missing Element	Rule (*= $\min(\text{death date, safety cutoff date, withdrawal of consent date})$)
day, month	
• If partial end date contains year only, set end date = earliest of 31DecYYYY or end date of the on-treatment period *
day	
• If partial end date contains month and year, set end date = earliest of last day of the month or end date of the on-treatment period*

Notice if imputed end date is less than the start date (if complete), use the start date as the imputed end date.

Any AEs and ConMeds with partial/missing dates will be displayed as such in the data listings.

For adverse events and any prior or concomitant medication, to decide whether the event or medication was prior or post-dosing is carried out as follows:

- If start date and time are not missing, then report as post-dosing if start date and time > dosing start date and time
- If start date is available, but not start time, then report as post-dosing if start date > dosing start date. This means that all events occurring on the dosing start day (even if they occurred prior to it) will be considered as post-dosing – similarly for medications, will be considered as concomitant.
- If both start date and time are missing, both adverse events and medications will be defined as being post-dosing.

